Adverse Events. Adverse events will be documented during the intervention and follow-up phase. AE's will be formally assessed at follow-ups by asking questions in the REDCap survey. During the intervention, AE's will be documented when a participant reports it to the weight loss counselor or posts it in the Facebook group. If it is reported during the intervention, the counselors will notify a research coordinator within 24 hours of learning of the event. UConn will then report it to the IRB (immediately if it's serious, or at the time of annual renewal). If participants gain 5% or more weight during the intervention, this will be treated as an adverse event. The participant will receive a phone call from a research coordinator, and they will be asked questions to figure out the cause of their weight gain. We will also assess Binge Eating Disorder (BED) at this time. If BED is present, we will treat it as a study-related AE. We will only assess BED once, even if there are multiple AEs for weight gain. Participants will not be removed from the intervention if they have 5% or more weight gain.

After we have completed all data analysis for the study, and it is put into a master dataset we will delete the Facebook group.

Measures

Data Collected	List of Measures	Screening/ Baseline	6-month pilot	F/up	Method
Inclusion/Exclusion criteria	Initial screening survey*	X			REDCap or Qualtrics
BMI	Height	X			REDCap
	Weight	X	X	X	REDCap
Demographics	Marital status, education, race/ethnicity, sexual orientation, work status, household income, household members*	X			REDCap
Binge Eating Disorder	SCID Eating Disorder Examination Questionnaire ⁴⁷		X**	X**	REDCap
Depression	Patient Health Questionnaire (PHQ-8 ⁴⁸)	X			REDCap
Weight Loss Problem Solving Skills	Social Problem-Solving Inventory-Revised (Modified for weight loss) ⁴⁹	X		X	REDCap
Group Climate Questionnaire	Group cohesion ⁵¹⁻⁵⁶			X	REDCap

Engagement	Facebook Engagement	X		Grytics into REDCap
App use	App use data*	X		WPI server and REDCap
Diet tracking	Data extraction*	X		MFP records
Usability Feedback	Acceptability, contamination, satisfaction, burden*, and user engagement ⁵⁰		X	REDCap and focus group

* = investigator derived

** = as needed for AEs

Psychometric properties for non-investigator derived measures:

SCID Interview for BED: The SCID's severity scales demonstrated substantial internal consistency (all Cronbach's alphas >.80), test-retest reliability, concurrent, and predictive validity.⁴⁷

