The Data and Safety Monitoring Plan will include monitoring the study for the progress of recruitment and retention, and the occurrence of adverse events (both serious and otherwise), inclusion/exclusion criteria, adherence to study protocols, and data review (completeness/outliers). Two safety officers will comprise the board.

I. Frequency of monitoring

During the pilot phase data reports will be reviewed and sent to the two safety officers once follow-ups have been completed and will include the following reports:

Recruitment rates and adherence to inclusion/exclusion criteria, and ethnic diversity goals:

Recruitment progress, including baseline characteristics, will be reviewed. This review will ensure that project deadlines are being met, that participants meet eligibility criteria, and that the ethnic diversity goals are being met. Recruitment progress is monitored weekly.

Adherence to study protocols:

Quality control will be conducted in all phases of the project. The Facebook group will be monitored daily for intervention protocol adherence.

Adverse events:

The adverse event report will include a listing of all adverse events including duration, severity, seriousness, relatedness, and action taken. Adverse events are documented throughout the intervention and at follow-up. In the event of a serious adverse event, the safety officers and IRB will be notified immediately.

Participant retention

Engagement will be tracked during the intervention, and completion of follow-ups will be documented. Participants will be reminded of upcoming study assessments. If a participant chooses to drop from the intervention, they will be given the option to skip the rest of the intervention, but still complete the follow-up. Retention is reviewed and discussed throughout the study and at follow-up.

Data review (completeness/outliers):

Data reports will be reviewed by the data manager, program director, statistician, and PI. Reports will include completeness of data; missing information within surveys; descriptive information for each endpoint without statistical testing; and quality control analyses for primary outcome. Data will be cleaned at the end of the study. A data review report will be provided to the IRB after the study is over and the team has time to create the report and sent off to the study sponsor (NIH).

II. AE reporting process

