Baseline participants who report conditions that could create a safety concern while receiving the intervention will be excluded. Adverse events that occur during the intervention will be assessed, recorded, and followed. Safety monitoring procedures will be documented in a standard protocol and overseen by the PI and coordinator. Any adverse events will be immediately reviewed by the coordinator. The safety officers will be informed of all adverse events during data review. Serious adverse events will be communicated immediately to the PI and safety officers. The NIH and UConn IRB will be notified immediately in the event of serious adverse event. Any death of a study participant will be reported to the NIH and UConn IRB whether or not it appears to be related to the study.

III. Safety Monitoring Committee

The two safety officers for this project will include faculty independent from the research team with expertise in clinical psychology, exercise and weight loss interventions, and an understanding of the types and severity of injuries commonly experienced during weight loss trials. The two safety officers will review the reports sent by the project director will use a checklist to document any corrective actions that should be communicated to the principal investigators, the University of Connecticut IRB, and the NIH. In addition, the safety officers may include documentation on whether the principal investigators should provide follow-up to a participant.

Privacy and Confidentiality

For the initial screening survey, participants can answer the questions at their own place and in an environment of their choice since it is done via a link online. If they do not want to finish, they can exit out of the survey whenever they would like. We also provide a simple information sheet prior to the survey so they can decide if they even want to move forward with doing the screening survey.

During the webinar process, UConn staff will go over all the details of the study and what it means to be a participant to give them a thorough description of what they can expect and what the study is so they can decide if this study is a good fit for them. During the webinar, they turn their video and audio off and choose where they view the webinar.

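### The safety officers' only routine report comes after follow-up, so their independent review of non-serious adverse events and trial conduct is too late to affect the intervention

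*Combined protocol and SAP*

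**What the plan says.** Data Safety Monitoring, I. Frequency of monitoring, fixes one time for routine reports to the two safety officers: "During the pilot phase data reports will be reviewed and sent to the two safety officers once follow-ups have been completed". The reports cover recruitment and eligibility, protocol adherence, adverse events, retention and data completeness. The recruitment item adds that this review will make sure that deadlines, eligibility criteria and ethnic diversity goals are met.

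II. AE reporting process states: "The safety officers will be informed of all adverse events during data review". Serious events have a separate, faster route, given in both subsections: "In the event of a serious adverse event, the safety officers and IRB will be notified immediately" and "Serious adverse events will be communicated immediately to the PI and safety officers". Within the study team, "Any adverse events will be immediately reviewed by the coordinator".

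III. Safety Monitoring Committee describes the officers as faculty independent of the research team. After reading the reports they use a "checklist to document any corrective actions that should be communicated to the principal investigators", the IRB and NIH. They may also record whether a participant should receive follow-up from the investigators.

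The Adverse Events paragraph under Methods singles out two kinds of event: "If participants gain 5% or more weight during the intervention, this will be treated as an adverse event", and, for binge eating disorder (BED) assessed at the resulting call, "If BED is present, we will treat it as a study-related AE".

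**The concern.** Independent oversight can change what participants experience only if it happens while they are being treated. Here the officers are asked to recommend corrective actions, yet for anything short of a serious event they receive their material when the intervention is over. A cluster of non-serious events, a run of weight-gain cases, a finding of BED not classed as serious, or a drift in protocol adherence would be known to the study team but to no independent reader on the committee.

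The early route also depends on an event being classed as serious, and the coordinator is the first to review each event. An event classed too low would not be seen independently until the end.

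**Working it through.** No sample size, power or event count is involved. The check traces each reporting route and sets it against the plan's calendar.

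**Routes**

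| Item | Study team | Safety officers | Source |
|---|---|---|---|
| Serious adverse event | Immediate | Immediate | Data Safety Monitoring, I and II |
| Non-serious adverse event | Immediate coordinator review; counselors notify within 24 hours | At data review | Data Safety Monitoring, II; Adverse Events |
| Weight gain of 5% or more | Coordinator call and BED assessment | At data review, unless serious | Adverse Events |
| BED found at that call | Recorded as related to the study | At data review, unless serious | Adverse Events |
| Recruitment and eligibility | Weekly | Report after follow-up | Data Safety Monitoring, I |
| Intervention adherence | Daily, in the Facebook group | Report after follow-up | Data Safety Monitoring, I |
| Retention | Throughout | Report after follow-up | Data Safety Monitoring, I |

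Subsection II does not date the data review. The only date given for material going to the officers is the one in subsection I, so the two are read together. The plan does not say who does the weekly and daily monitoring; the study team is the natural reading.

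The IRB does not reliably fill the gap. The Adverse Events paragraph sends non-serious events to it at annual renewal, and the study lasts about nine months. The approval date is not given, so renewal may or may not fall within the intervention.

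**Calendar**

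Inputs from the Study Timeline table: recruitment December to February, intervention February to July, follow-ups July to August. The plan gives no report date, so the end of August is assumed as the earliest date after follow-ups.

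Delay = report date − event date.

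- February event: from 1 February to 31 August is about 7 months; from 28 February, about 6 months.
- July event: from 1 July to 31 August is about 2 months; from 31 July, about 1 month.
- Serious event at any time: no planned delay.
- Recruitment and eligibility: the report arrives about 6 months after recruitment closes at the end of February.

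**With one added report at the midpoint (end of April)**

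- February event: from 1 February to 30 April is about 3 months; from 28 February, about 2 months.
- May event, the first month to wait for the final report: from 1 May to 31 August is about 4 months; from 31 May, about 3 months.

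The longest wait falls from about 7 months to about 4, and events from February to April are read independently while the intervention is still running.

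**The case against.** The strongest case against is that the plan is proportionate. It describes the risks as minimal, suggests only moderate exercise and screens out risk conditions. Both arms receive the same counselor-led program and differ only in the app. Serious events reach the officers at once, and the two named events already have a response during the trial: weight gain of 5% or more prompts a call and a BED assessment. As this is a pilot, end-of-study comments on recruitment, adherence and retention can still improve the later efficacy trial. No requirement in the documents is breached.

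Much of this stands, and it rules out two stronger readings.

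- A reader might infer that the monitoring and corrective actions can reach no participant, so that none of the 70 could benefit. The documents do not support that. Serious events can lead to action during the trial, and the study team acts in real time. A recommendation that a participant receive follow-up can also be carried out after the last assessment, at least until the link between ID and identity is destroyed once the master dataset is saved.
- A reader might infer that the subsections contradict each other. They do not, strictly: an end-of-study report can be read and a checklist completed exactly as written. They fit poorly, because a report at that time cannot secure deadlines or eligibility in this trial, and corrective actions cannot alter an intervention that has ended.

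The objection does not supply independent review of non-serious events and conduct during the intervention. The real-time work is done by the team running the trial, which is the gap that independent officers exist to fill.

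**Conclusion.** The point holds in this limited form: independent review of non-serious adverse events, and of eligibility, adherence and retention, is scheduled only after follow-up and so cannot affect the 6-month intervention. Serious adverse events are outside the point.

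The planned delay for a non-serious event is about 1–2 months (July) to about 6–7 months (February). This rests on the Study Timeline calendar, which the plan calls subject to change, and on the assumed report at the end of August; a later report lengthens every figure. The documents give no expected number of non-serious events, so the number of participants affected cannot be stated. With risks described as minimal, this is an inexpensive improvement in oversight rather than a defect that undermines the trial.

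**What to change.** In I. Frequency of monitoring, add at least one report to the safety officers during the intervention, for example at its midpoint, and keep the final report. Use the same descriptive content: the adverse event listing, including weight gain of 5% or more and any BED findings, with retention and protocol adherence. Do no between-arm testing; the analysis plan is then unaffected.

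Reconcile the surrounding text. A midpoint report still follows the close of recruitment, so the assurance about deadlines, eligibility and diversity should be attributed to the weekly monitoring rather than to the officers' report. II. AE reporting process should say when the data review takes place. III. Safety Monitoring Committee should say which corrective actions are meant for this intervention and which for the later trial. If the sponsor keeps review at the end only, the plan should say so, give the reason, and drop the assurance.

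The cost is one extra listing from data already being recorded, and one extra read by two officers already in the plan.
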